- The R&D Application Department Level Review eCRAF Form serves a major function for section and department level review and may result in this study not being permitted due to resources, scientific validity, or other reasons.
- You must submit a copy of the signed R&D Application Department Level Review eCRAF Form with this IRB application in the supplemental document section.
- Failure to complete the steps in the above order will result in a significant delay in the IRB's review of this study.

- Acknowledged

6.0

Funding Information and Outside Services

6.1 Select the applicable funding source(s).

- None (no money, equipment, supplies, and/or services will be provided by external source)
- No monetary funding BUT equipment, supplies, and/or services will be provided
- Federal Government
- Foundation or Non-profit
- Industry/Commercial Sponsor
- State or Local Government
- Investigator or Departmental/Unit Funds
- Carilion RAP Grant
- Other

Select all the Federal funding sources that apply:

- National Institutes of Health (NIH)
- National Science Foundation (NSF)
- Department of Agriculture
- Department of Commerce
- Department of Defense

- Department of Education
- Department of Energy
- Department of Energy, Office of Science, STTR
- Department of Energy, Office of Science, SBIR
- Department of Health and Human Services
- Department of the Interior
- Department of Justice
- Department of Transportation
- Environmental Protection Agency
- National Institutes of Standards and Technology
- U.S. Air Force Office of Scientific Research (AFOSR)
- U.S. Army Research Office
- U.S. Navy Office of Naval Research
- Other

Please provide more detailed information about the funder, as applicable, including funder name or department (including name of NIH institute, center, or offices, name of NSF directorate, etc.).

iTHRIV award

Award / Contract Status:

awarded

Grant Title, if applicable:

A Comparison of the Effectiveness of Telepsychiatry with a Randomized Waitlist Control Utilizing Patient Reported Outcome Measures (PROMs)

6.2 Select services from all areas outside of the Research Team members' affiliations that are necessary to conduct the work.

Research and Development (R&D) will contact you to arrange a Feasibility Meeting based on your responses below. This will ensure roles, responsibilities, and costs associated with this project are understood by all parties. Final sign-off from leadership in the additional service areas, as well as contracts, may be required.

- Animals
- Basic Science Laboratory Services
- Center for Simulation, Research & Patient Safety (CSRPS)
- Department of Medicine
- Department of Pediatrics
- Department of Psychiatry
- Department of Surgery
- Emergency Department
- Hazardous Materials
- Health Analytics Research Team (HART), including Epic Data Extraction, Statistics Services, Carilion RedCap, Epic Research Access
- Human Resources
- Jefferson College
- Nuclear Medicine
- Nursing
- Pathology
- Pharmacy
- Physical Therapy
- Radiology
- Recombinant DNA/RNA
- Respiratory
- Solstas Lab
- Technology Services Group (TSG)

Other
 None

Please specify:

VT Psychology

6.3 You have selected that HART services are needed for this research. Specify the resources needed.

Epic Data Extract
 Statistics Support (biostatisticians)
 Carilion REDCap (Data management)
 Epic Research Access for Chart Review
 TriNetX Identifiable Patient List/Data Set
 SPARC Carilion Secure Research Environment

Note: If you have not yet discussed this project with the HART team, please contact them at [contact] before proceeding any further with this application. This will ensure that your request for this project is feasible.

7.0 Regulatory Compliance

7.1 How many studies is the PI currently responsible for?

2

7.2 Does the PI have protected or dedicated time available to conduct this research?

Yes No

7.3 Has any member of the research team ever received a FDA 483, "Warning Letter", Notice of Disqualification, or other warning or disciplinary action from an agency or licensing authority?

Yes No

7.4 Has this study been disapproved or terminated by another IRB?

Yes No

8.0 Conflict of Interest

8.1 A Conflict of Interest, per the Carilion Clinic Organizational Policy, is a situation in which an Investigator's and/or their Family Member's financial, professional, or other personal consideration may directly or indirectly affect, or reasonably appear to affect, the Investigator's professional judgement in performing their Institutional Responsibilities. A Conflict of Interest may be actual, apparent, or potential. Any research team member listed on the IRB application is considered to be an Investigator. It is the Principal Investigator's responsibility to query all Carilion research team members on this study to ensure they have honestly completed their Annual COI Disclosure and that it is current. The Principal Investigator should be notified by the study team member if the study team member has disclosed any related interests. Carilion Clinic's Conflicts of Interest in Research Policy can be found [here](#).

If this study has any external funding or support, have all Carilion research team members filed an Annual COI Disclosure through Carilion Clinic's Office of Organizational Integrity and Compliance via the COI-Smart online disclosure system?

Yes
 No
 N/A - this study does not have any external funding or support

Do any Carilion research team members or their family members have a Conflict of Interest or related outside interest with the sponsor/funding agency of this study?

Yes No

It is the Principal Investigator and conflicted employee's responsibilities to ensure the conflict or any changes that result in a potential conflict are disclosed to the Office of Integrity and Compliance who will refer it to the Carilion Clinic's Research Conflict of Interest Committee for appropriate management when necessary. Disclosure and management must occur before the conflicted employee is permitted to engage in any research activities. Any employee who violates the Conflict of Interest policy is subject to disciplinary actions, up to and including termination.

9.0

Collaboration

9.1 Is this research project a collaboration between Carilion Clinic and another institution (including, but not limited to Fralin Biomedical Research Institute at VTC, VTCSOM, VT, UVA)?

Yes No

9.2 Please provide the name(s) of the collaborating institution(s) and the name(s) and contact information of the lead PI(s) at that institution.

[name]., (Co-PI)
Clinical Associate Professor, Department of Psychology

9.3 Is Carilion acting as one site of a multicenter study?

Yes No

9.4 Will the multicenter protocol be followed as written or are there components or aspects of the research that this site will not participate in or that will be modified?

(Ex: local site will not recruit into one of the cohorts or into a sub-study; the age range will be narrowed, a specific procedure or test isn't available locally so another will be performed, etc.)

- The protocol will be followed as written.
- The protocol will be modified locally.

Department of Psychology
Virginia Tech
[contact]

research design, data management, data analysis (de-identified), scholarly products**9.9 If this study has any external funding or support, do the external collaborators' institutions possess a PHS-Compliant FCOI policy?**

Yes
 No
 N/A - study does not have external funding or support

9.11 Describe any plans for initial and ongoing training of the other sites on important aspects of the protocol.

We meet weekly to review study progress, data acquisition and trends with focus on maintaining protocol procedures without deviation

9.12 Describe the plan to manage communication of information at the other sites that is relevant to the conduct of the research and the protection of human subjects, such as reporting of unexpected problems, protocol modifications, and interim results for all sites to the Carilion Clinic IRB.

For FDA-regulated clinical trials, the plan must include the plan for reporting serious adverse events or serious adverse device effects, significant new risk information, and any other reports mandated by regulation or policy.

We meet weekly to review study progress, data acquisition and trends with focus on maintaining protocol procedures without deviation

The PI or other Carilion IRB-approved team member will report any unexpected problems, protocol modifications and interim results to the Carilion Clinic IRB

9.13 Describe the Carilion Clinic investigator's plan for oversight of research activities at other sites including verification of Institutional approvals, data safety monitoring, and ensuring data quality and integrity.

For FDA-regulated clinical trials, the plan must include the use of trained and qualified monitors to oversee the progress of the research.

The study team meets weekly to ensure approvals, monitoring and data quality and integrity are maintained

9.14 Will identifiable data or specimens be transferred, transmitted, or shared outside of Carilion?

For example, transfer of data or specimens from Carilion Clinic to an external collaborator (including VT, VTCRI, UVA, etc.).

Yes No

9.15 Provide information about the types of specimens and/or data, including specific datapoints, that will be shared and the methods of storage of the data at the collaborating site. Include a description of the process for shipping the specimens and/or transmitting the data to the collaborator, including the method of encryption if sharing data electronically.

Data collection will be entered into REDCap by [name] (Psychiatry Intake Coordinator) and reviewed by the PI or sub-investigator. [name], a VT Psychology graduate student, will be the data manager for the project. Thus, we request that she have access to REDCap data, without PHI access.

Data in REDCap that would be visible to [name] at VT would be:

subject number
randomized group (no intervention or minimal intervention)
date of assessment by [name] will be put as day 1 NOT a specific date of appointment
PHQ-9, GAD-7, BASE-6, USAUDIT, DAST-10 scores

Covid Event Checklist (positively checked answers with respect to COVID infection, prevention, negative mental health effects of Covid, SDOH and resiliency factors) - there are no dates or identifying information in this checklist, simply the check-marked items themselves
Adult Behavioral Health Screen (ABHS) (marked as completed or not)

The VT collaborator would not have access to any of the 18 HIPAA identifiers.

Data from REDCap will be exported to SPARC by HART and de-identified to allow other non-Carilion study members ([name]) to analyze data that is de-identified.

10.0

Human Subjects Research Description

10.1 In the opinion of the Principal Investigator, does this research impart minimal risk or greater than minimal risk to subjects?

As defined by regulation, minimal risk means that the probability and magnitude of harm or discomfort anticipated in the research are not greater in and of themselves than those ordinarily encountered in daily life or during the performance of routine physical or psychological examinations or tests. Please note that the IRB makes the final determination of risk level and may ask you to change this based on their decision.

If this is a Conversion of a Paper Application, select the risk level that has been determined already by the IRB at most recent review per the most recent approval letter (expedited review = minimal risk, full board review = greater than minimal risk).

- Minimal Risk
- Greater than minimal

10.3 Select ALL the types of research activities that will be involved in your human subject research subject, or select None.

- Drugs, biologics or other FDA-regulated products (other than devices)
- Medical devices
- Review of data/records (i.e. prospective clinical data collection from medical records, reviewing previously collected data)
- Biospecimen collection (i.e. blood, tissue, urine, saliva)
- Analysis of existing specimens from patients and/or bank or repository
- Human genetic analysis or Recombinant DNA, or Gene Therapy
- Invasive medical procedures (i.e. lumbar puncture, biopsy, endoscopy, surgery, etc.)
- Non-invasive medical procedures routinely employed in medical practice (i.e., physical measurements, EKG, EEG, moderate exercise, etc.)
- Imaging (i.e., x-ray, CT, DEXA, MRI, ultrasound, etc.), Use of Therapeutic or Diagnostic Radiation, Radioactive Drugs
- Task-based activities or games, or Psychometric Testing
- Surveys, questionnaires, focus groups, or interviews
- Examination of educational practices, instructional techniques, curricula or classroom management
- Observations of public behavior
- Interventions or procedures involving deception
- Use of Internet
- Audio or Video recording
- International Research
- NONE OF THE ABOVE

10.4 Briefly describe the proposed research in language that can be understood by a non-scientist.

This description should summarize the objectives of the research and the procedures to be used, with an emphasis on what will happen to the subjects. If this is an application for the establishment of a research repository, summarize the objectives of the repository and how data/specimens will be used in the future.

The utilization of patient reported outcome measures (PROMs) during in-person care allows for on-going assessment of the severity of mental illness and patient outcomes across treatment (Lewis, et al., 2019; Douglas, et al., 2020). Additionally, it provides immediate feedback on the patient's psychiatric status to both the patient and practitioner (Lambert, et al., 2018). Carilion Clinic - Psychiatry & Behavioral Medicine (CC-P&BM) ambulatory clinic implemented PROMs prior to the start of the COVID-19 pandemic and continues to utilize them as part of patient care. All new patients are asked to complete an initial PROM bundle of assessments twenty-four hours before their initial appointment, including the Brief Adjustment Scale (BASE-6), Patient Health Questionnaire (PHQ-9), Generalized Anxiety Disorder survey (GAD-7), US Alcohol Use Disorder Identification Test (USAUDIT), and Drug Assessment Screening Test (DAST-10). Automatic monthly reminders to complete the BASE-6, PHQ-9 and GAD-7 continue after the first visit with the clinician.

The COVID-19 pandemic necessitated a rapid transition nationally from in-person to telemedicine (Augsterfer, Mollica, & Lavelle, 2018; Torous & Wykes, 2020; Kalin, et al., 2020), a change that occurred in our clinic as well. Over the last 2 years, research members of Carilion Clinic Psychiatry and Virginia Tech Psychology departments have been actively using PROM data to assess psychiatric health outcomes before and after the outbreak of COVID-19 in the United States. Initial results indicate that patients who received care via telemedicine not only **did not experience worsening symptoms, but showed improvements in depression, anxiety and psychological functioning**. However, without a control group of untreated patients to compare, the impact of telemedicine plus PROMs remains unclear. A wait-list control group design would allow us to compare patients receiving telemedicine and repeated completion of PROMs (current practice) to patients referred to psychiatry, but not receiving telemedicine treatment or completing PROMs during the same time period. We propose randomizing wait-list individuals to one of two groups to assess the influence of time alone awaiting initial psychiatric clinician assessment (no intervention) versus minimal intervention using repeated PROMs and microlearning patient education videos while awaiting initial psychiatric clinician assessment. This kind of design allows assessment for the influence of time and the type of health service contact that replicates the basics of measurement-based psychiatric services (measurement of symptomology and well-being), but with none of the benefits of psychiatric supports, interventions, and techniques.

10.5 Provide background information about the research question(s.) Explain why the research is needed and include the relevance of this research to the contribution of this field of study.

Please include the current state of knowledge about your project topic by summarizing and synthesizing the available research (including published data) to provide justification for the study. Include a reference list of literature cited to support the protocol statement, either in your response below or as a supplemental document as part of the application packet.

Patient-reported outcome measures are a component of Measurement-Based Care (MBC) that involves collaboration between patient and clinician using structured evaluations of patient symptoms to inform behavioral health treatment and clinical decisions (Lewis, et al., 2019). In clinical settings, MBC has been found to improve outcomes and decrease dropout (Lambert, et al., 2018). Since patient-reported outcome measures can be performed by patients or clinicians, in session or out of session, and in-person or via telemedicine, their application is particularly pertinent during or after a crisis (Augsterfer, Mollica, & Lavelle, 2018). The COVID-19 pandemic abruptly accelerated the transition to telehealth for many and necessitated alterations to traditional therapeutic means (Torous & Wykes, 2020; Kalin, et al., 2020). PROMs are a tool that can improve the telehealth experience by strengthening patient-clinician relationships strained by the use of telemedicine, and allows for tracking of patient symptoms, which can be discussed and intervened upon in session (Douglas, et al., 2020).

Over the last 2 years, research members of Carilion Clinic Psychiatry and Virginia Tech Psychology departments have been actively using PROM data to assess psychiatric health outcomes *before and after the outbreak of COVID-19* in the United States (IRB approved protocol 20-905). Initial results indicate that patients who received care via telepsychiatry not only **did not experience worsening symptoms, but showed**

improvements in depression, anxiety and psychological functioning. However, without a control group of untreated patients to compare, the impact of telemedicine plus PROMs remains unclear. A wait-list control group design would allow us to compare patients receiving telemedicine and repeated completion of PROMs (current practice) to patients referred to psychiatry, but not receiving telemedicine treatment or completing PROMs during the same time period. We propose randomizing wait-list individuals to one of two groups to assess the influence of time alone awaiting initial psychiatric clinician assessment (no intervention) versus minimal intervention using repeated PROMs and reviewing microlearning patient education videos while awaiting initial psychiatric clinician assessment. This kind of design allows assessment for the influence of time and the type of health service contact that replicates the basics of measurement-based psychiatric services (measurement of symptomology and well-being), but with none of the benefits of psychiatric supports, interventions, and techniques.

As of July 2021, **32 Carilion psychiatric clinicians** are engaged in Owl Insights, an MBC vendor. Approximately **500 unique individuals complete monthly PROMs** through this system as part of routine clinical care. Our research group recently conducted analyses of nearly 900 ambulatory adult psychiatric patients in ambulatory psychiatry at Carilion Clinic (CC&PBM) engaging in PROMs via telepsychiatry and in-person modalities. PROM results of a patient cohort in clinical care prior to the onset of COVID-19 (November 2019) through March 2021 demonstrated that depression, anxiety and psychological functioning did not decline as hypothesized but statistically improved (Kablunger, et al., 2021). Data also show that the **engagement rates range from 33 to 74% depending on demographic factors**, and completion rates were significantly different for diagnostic group and payor status of the patient (Kablunger, et. al, 2021). The standard goal for MBC utilization is 80%, while the department goal is to have **all** patients participate in PROM completion. Our research group has also completed focus groups of psychiatric clinicians and staff with regards to Owl Insights and PROMs within the past year, identifying barriers and facilitators to its use and plan training implementation for improved adherence and satisfaction (summary of focus group data and training outline- included in grant application, IRB approved protocol 20-1065). Since March 2020, CC-P&BM has been engaging with patients via telephone and several telehealth platforms. Currently, ambulatory psychiatry uses AmWell, a telehealth platform that provides secure telemedicine visits between clinician and patient. The department has documented between **2100-2300 adult telemedicine sessions monthly and 200-700 in-person visits per month** between June 2020 and June 2021.

CC-P&BM currently has a wait-list of over 300 adults referred for mental health evaluation and treatment. Access to psychiatric clinicians remains insufficient despite increasing numbers of providers in our clinic and the mental health needs associated with the pandemic are rising. As a result, a clinical intake coordinator (Licensed Professional Counselor) began in the CC-P&BM ambulatory clinic September 2021. This coordinator will individually contact people on the wait-list for psychiatric care by phone as part of routine care, beginning with the referrals most remote in time. The coordinator will complete an intake assessment for each wait-list individual who wants a psychiatric referral. Prior to the initial intake assessment by the intake coordinator, wait-list individuals will receive a bundle of PROMs automatically (through Owl Insights) to complete. These measures include the PHQ-9, GAD-7, BASE-6, DAST-10, USAUDIT, Covid Event Checklist and the Adult Behavioral Health Screen (ABHS), all of which are currently used in routine ambulatory care. The intake coordinator will complete the intake assessment, noting the completion, and scores of, the PROMs. Scores of the PHQ-9, GAD-7 and BASE-6 will be utilized to triage the most severe referrals and move them up for a sooner appointment (the triage system of scores and Nurse-Practitioner vs Medical Doctor screening questions are attached to this application). Any concern about patient safety is also addressed immediately during this intake and is also noted in the materials attached to this application. **Up to this point, all intake coordinator/referral interaction are part of routine care.**

If eligible and capable of consent based on intake coordinator clinical judgement, individuals will then be randomized to participate to the no intervention group (completion of screening PROMs only during the intake coordinator assessment) or the minimal intervention group (intake coordinator assessment, including PROM screening and then prospective monthly PROM completion in addition to assigned microlearning

patient education videos). We will analyze changes in PROM scores for individuals engaged in both wait-list groups and compare results to their PROM scores at the initial provider telemedicine visit and over time (6 months post first provider assessment). Consent may be in-person with hard copy consent forms and signatures or through e-Consent either in-person using ipads or remotely using REDCap.

10.6 State the research hypothesis or the question that the research will answer.

List the research objectives and expected outcomes. A primary outcome or objective must be identified. After the statement of the primary objective, secondary objectives may be listed. Objectives should be simple and specific.

Aim 1 will use PROMs to assess the symptomology and well-being of adult individuals on a wait-list group referred to CC-P&BM clinic from their initial referral to their initial psychiatric session.

In particular, we propose randomizing wait-list individuals to one of two groups to assess the influence of time alone awaiting initial psychiatric clinician assessment (no intervention) versus minimal intervention using prospective monthly repeated PROMs and viewing microlearning patient education videos while awaiting initial psychiatric clinician assessment.

Aim 2 will use PROMs to determine whether there is a difference in clinical symptomology and well-being for patients during telemedicine treatment with their practitioner compared to wait-list individuals.

10.7 State how qualitative and/or quantitative data will be analyzed in order to answer the research questions.

Include an analysis from a statistician (or someone familiar with statistical methods) that either indicates the power calculation for the sample size necessary to meet the primary study outcome or objective OR a statement from the statistician indicating reasons why a power calculation is waived or not necessary for this study. Also include the statistical test(s) that will be used to analyze your primary study objective (t-test, chi-square, etc.). Secondary outcomes may be listed as descriptive.

If this is a proof of concept or feasibility study that includes limited efficacy testing, please provide a description on how your design will determine if an intervention should be recommended for broader efficacy testing. If a study is meant to be solely descriptive, then the primary outcome or objective must be limited in scope. As such, the study results apply only to the sample being studied, and conclusions cannot be drawn about the larger population.

This is required for ALL studies, as this section helps the IRB confirm the data being collected are relevant to the study aims and planned analysis.

The primary outcome of interest is the change in total PROM score for each assessment required of patients enrolled in the study. Initial PROM scores will be acquired and assessed after referral into the CC-P&BM program. The potential to receive few records per patient is believed to be relatively high; therefore, the final PROMs completed for each assessment will be used to determine the change in total score. This change will be compared between patients receiving telemedicine and those of the control (wait-list) groups. A two-sample t-test or non-parametric equivalent of the mean change in total PROM will be performed to determine if the change is significantly different among treatment types. An alpha of 0.05 will be used to assess statistical significance. Univariate and multivariate analyses may occur to measure numeric variables by measures of central tendency and variation and categorical variables by frequencies and percentages. Trends of PROM scores will be evaluated between treatment types by the time in program.

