2. Randomly assign patient into group (REDCap will do this when you start a new patient record); inform patient of the group they have been randomly assigned into to provide further instructions.
3. Provide all patients with CONNECT phone number at termination of the call.

Initial consenting process occurs after routine clinical psychiatry intake assessment by intake coordinator (if intake coordinator assesses that patient has capacity to pursue study discussion): 30-45 min consent process through REDCap or hard copy in-person. REDCap will be utilized to perform randomization. There is no blinding due to the nature of the wait-list control groups; both patients and investigators will be aware of study group assignment.

No intervention group randomization: no additional time/study procedures occur after consent; **SO C monthly PROMs DO NOT begin until after initial psychiatric provider evaluation for 6 additional months.**

Minimal intervention randomization: each month PROMs including PHQ-9, GAD-7 and BASE-6 are sent automatically for subject to complete via email or cell phone before initial psychiatric provider appointment - takes approximately 15 minutes to complete; watching microlearning videos about illness/symptoms takes approximately 15-30 minutes to watch depending on # videos recommended. Current wait-time for patients to see MD provider is 3-4 months; therefore, subjects in the minimal intervention group will participate in the study for up to 6 months before beginning regular treatment with provider.

PROM data from both groups will continue at initial psychiatric provider evaluation and monthly as is current clinical practice. Therefore, an additional 6 months of PROM data for each group will be followed to assess the research question of whether a no intervention or minimal intervention group may provide benefits to patients waiting to be seen and followed by psychiatric providers.

Total study participation time = 6-12 months depending on length of wait time before first psychiatric provider appointment

You must attach surveys, instruments, interview questions, focus group questions, etc. in the Initial Submission Packet and label them clearly.

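### The same-period comparison of telemedicine with untreated referrals promised in 10.4 and 10.5 does not exist in the design; treatment always follows the wait, so Aim 2 confounds treatment with time since intake

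*Combined protocol and SAP*

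**What the plan says.** - **Rationale (10.4, repeated in 10.5).** The clinic's earlier telemedicine data lacked an untreated control group. A wait-list design is said to supply one by comparing telemedicine patients with "patients referred to psychiatry, but not receiving telemedicine treatment or completing PROMs during the same time period".
- **What is randomised (10.4, 10.5, 10.6).** "We propose randomizing wait-list individuals to one of two groups to assess the influence of time alone awaiting initial psychiatric clinician assessment", against monthly PROMs plus education videos during the same wait. No group is assigned to start telemedicine at once.
- **Aim 2 (10.6).** To "determine whether there is a difference in clinical symptomology and well-being for patients during telemedicine treatment with their practitioner compared to wait-list individuals".
- **Source of the treated data (10.5).** Changes in both wait-list groups are to be analysed, and the investigators will "compare results to their PROM scores at the initial provider telemedicine visit and over time".
- **Sequence (19.1).** "Current wait-time for patients to see MD provider is 3-4 months", with up to 6 months allowed for in the minimal-intervention group. Then "PROM data from both groups will continue at initial psychiatric provider evaluation and monthly as is current clinical practice", for 6 further months in each group.
- **Analysis (10.7).** Change from the post-referral PROM to the final PROM is compared between telemedicine and wait-list patients by a two-sample t-test or a non-parametric equivalent, at alpha 0.05. PROM trends by time in program are also to be evaluated, with no model specified.

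**The concern.** The gap the trial is meant to fill is that improvement under telemedicine was seen without an untreated group followed over the same months. A no-intervention group does exist here, but only while everyone else is also waiting. When treated data begin to accrue, both groups have moved into care. The telemedicine contrast is therefore later months against earlier months, and any change that comes with time since intake enters the estimate.

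10.7 names this contrast as the comparison of the primary outcome, and the grant title in 6.1 describes telepsychiatry compared with a randomised wait-list control. A reader would take the result as a randomised estimate of the effect of telemedicine. It would be a before-after comparison, which is the weakness that 10.4 says the trial was meant to cure.

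**Working it through.** **1. Is there a concurrent untreated comparator anywhere?**

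| Candidate | Where | Concurrent with treated follow-up? |
|---|---|---|
| No-intervention group | 10.5, 19.1 | No. It waits, then is treated like the other group |
| Minimal-intervention group | 10.5, 19.1 | No. Same sequence |
| Standard-of-care records, 11.1.21 to 4.5.22 | 11.5, 13.3, 16.1 | No. They end before consented enrolment starts on 4.6.22 |

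Staggered enrolment means that on a given calendar date some participants are waiting and others are treated. They are then at different times since intake, and 10.7 makes no use of the overlap.

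**2. Does the planned test separate treatment from time?** No. A two-sample t-test on change has no term for time since intake. Pairing the data, or making the windows equally long, would not alter the order.

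**3. Can the direction or size of the bias be stated?** The plan gives no effect size, SD or natural course, so there is no figure to reproduce. The course below is assumed throughout, and the true telemedicine effect is set to zero.

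- Natural improvement by month *t*: f(t) = A(1 − 0.5^(t/h)), with A the total points and h the half-life in months; or a linear course of 0.3 points per month.
- Wait W = 3.5 months, the middle of the 3-4 months in 19.1.
- Bias = apparent telemedicine improvement minus wait improvement. Positive favours telemedicine.

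Three readings of the comparison:

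- (a) from the first visit, equal window: [f(2W) − f(W)] − f(W)
- (b) from the first visit, the 6 months of 19.1: [f(W+6) − f(W)] − f(W)
- (c) from the intake PROM to the final PROM, one reading of 10.7: f(W+6) − f(W)

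Worked case, A = 4, h = 4. The powers are 0.5^(3.5/4) = 0.545, 0.5^(7/4) = 0.297 and 0.5^(9.5/4) = 0.193.

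- Wait improvement: 4 × (1 − 0.545) = 1.82
- (a) 4 × (0.545 − 0.297) − 1.82 = 0.99 − 1.82 = −0.83
- (b) 4 × (0.545 − 0.193) − 1.82 = 1.41 − 1.82 = −0.41
- (c) 4 × (1 − 0.193) − 1.82 = 3.23 − 1.82 = +1.41

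| Assumed course | (a) | (b) | (c) |
|---|---|---|---|
| A = 4, h = 2 | −1.98 | −1.77 | +1.04 |
| A = 4, h = 4 | −0.83 | −0.41 | +1.41 |
| A = 4, h = 8 | −0.27 | +0.15 | +1.20 |
| Linear, 0.3 per month | 0 | +0.75 | +1.80 |

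Linear row: the wait gives 0.3 × 3.5 = 1.05; (a) 1.05 − 1.05 = 0; (b) 0.3 × 6 − 1.05 = 0.75; (c) 0.3 × 9.5 − 1.05 = 1.80. Linear worsening at the same rate reverses these signs.

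With no treatment effect at all, the sign changes across a row (choice of baseline and window) and down column (b) (choice of course).

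**The case against.** **The treated group may be other people.** 10.7 reads as a test between two sets of patients, 10.4 calls telemedicine with PROMs current practice, and 10.5 mentions about 500 people completing monthly PROMs. The point that the source is not stated cleanly stands. But 10.5 refers the comparison back to the participants' own later scores, and the only other cohort in the eligibility criteria is the earlier standard-of-care one. If a separate cohort is meant, the contrast is still non-randomised, with selection as the problem in place of order.

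**The plan does consider time.** 10.4 says the design assesses the influence of time, and 10.7 promises trends by time in program. The first is about the two wait-list groups. The second names no model or adjustment.

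**The later 6 months also serve the randomised comparison.** This is correct. 19.1 uses them to ask whether either wait-list condition brings benefit, and that question is untouched.

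**A stronger reading is tempting.** A reader might infer that natural improvement falls in the wait, so that telemedicine is biased to look worse, with a high false-positive rate. The documents do not support this. They give no natural course, equal windows give zero bias under a linear course, and a change taken from intake can favour telemedicine. The coordinator also starts with the most remote referrals (10.5, 13.5), so early recovery may be over before the intake PROM. If intake came 3 months after referral (an assumption), the A = 4, h = 4 figure in (a) would shrink by 0.5^(3/4) = 0.59, from −0.83 to −0.49. Any false-positive rate would also need an SD and a paired equal-window test, and the plan contains neither.

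**Conclusion.** The point holds as a mismatch between a stated design property and the design. The documents alone show it: a same-period untreated comparator for telemedicine is promised, only wait-list conditions are randomised, and treatment always follows the wait. The unadjusted t-test in 10.7 therefore cannot separate treatment from time since intake.

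No single size or direction can be attached. Under the assumed courses the bias runs from −1.98 to +1.80 points with a true effect of zero, which shows only that the result is not interpretable as it stands. Aim 1, the concurrent randomised comparison of no intervention with minimal intervention, is not affected. This should be corrected before analysis. It does not call for a change in how the trial is run.

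**What to change.** **10.4 and 10.5.** Replace the same-period claim with a statement such as:

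> Aim 2 is a non-randomised before-after comparison of the wait with the period after the first provider visit. It has no concurrent untreated control. Randomised causal conclusions are limited to the two wait-list groups.

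**10.6 and 10.7.** Label the telemedicine contrast observational, state whose PROMs form the treated data, and do not rest Aim 2 on the unadjusted t-test. Fit one repeated-measures mixed model per scale (PHQ-9, GAD-7, BASE-6) to the PROMs already collected, with:

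- months since intake as a flexible term;
- randomised arm, because the monthly PROMs during the wait come only from the minimal-intervention group, whose condition may itself have an effect;
- intake score, triage tier and tier-by-month;
- an indicator for treatment started, set to zero for the PROM completed before the first visit;
- months since the first visit, so that gradual benefit is captured;
- a participant random effect.

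The last fixed term matters. Suppose the benefit is 0.5 points per month, which averages 0.5 × (1+2+3+4+5+6)/6 = 1.75 points over six months. In simulated checks under assumed courses, a model with only the on/off indicator returned about 0.2 to 0.3 points.

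Report the model as a supportive estimate that assumes wait length is ignorable given these covariates. The assumption is a real one: 10.5 and 23.5 let severity shorten the wait, and clinical changes after intake are not fully covered by intake score and tier.

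**Cost.** Protocol and SAP wording, and a standard model with no new visits or questionnaires. The analysis file must carry months since intake for each PROM. 9.15 shows the collaborator a day 1 code in place of dates, so relative days need to be kept. The downside is a wider interval for telemedicine and a more modest claim.
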